4. IRB APPROVAL AND FDA AMENDMENTS

The Investigator will obtain, from the University of Pittsburgh Institutional Review Board (IRB), prospective approval of the clinical protocol and corresponding informed consent form(s); modifications to the clinical protocol and corresponding informed consent forms, and advertisements (i.e., directed at potential research subjects) for study recruitment.

The only circumstance in which a deviation from the current IRB-approved clinical protocol/consent form(s) may be initiated in the absence of prospective IRB approval is to eliminate an apparent immediate hazard to the research subject(s). In such circumstances, the Investigator will promptly notify the University of Pittsburgh IRB of the deviation. The Investigator should also notify the sponsor of this event.

The University of Pittsburgh IRB operates in compliance with FDA regulations at 21 CFR Parts 50 and 21 CFR 56, and in conformance with applicable International Conference on Harmonization (ICH) Guidelines on Good Clinical Practice (CGP).

In the event that the University of Pittsburgh IRB requires, as a condition of approval, substantial changes to a clinical protocol submitted under an FDA-accepted IND application, or in the event of the Investigator's decision to modify the previously accepted clinical protocol:

- The Sponsor will submit (i.e., in advance of implementing the change) a Protocol Amendment to the IND describing any change to a Phase 2 protocol that significantly affects the safety of subjects, the scope of the investigation, or the scientific quality of the study. Examples of Phase 2 clinical protocol changes requiring the submission of a Protocol Amendment include:
 - Any increase in drug dosage or duration of exposure of individual subjects to the investigational drug beyond that described in the current protocol, or any significant increase in the number of subjects under study.
 - Any significant change in the design of the protocol (such as the addition or deletion of a control group).
 - The addition of a new test or procedure that is intended to improve monitoring for, or reduce the risk of, a side effect or adverse event; or the dropping of a test intended to monitor the safety of the investigational drug.

5. RECRUITMENT AND INFORMED CONSENT PROCEDURES

5.1 RECRUITMENT METHODS:

PCAS physicians are generally alerted to incoming resuscitated cardiac arrest patients either through a med call page (to accept the patient in transfer) or a page from emergency medical services stating the patient is en route to the emergency room (ER). PCAS physicians will review details of the patient's cardiac arrest to determine eligibility in consultation with a study coordinator. The ultimate designation of whether a patient is eligible will require a physical exam to determine neurologic function and hemodynamic stability upon ER presentation. If a patient is deemed eligible, they will be enrolled into the trial. We are requesting a waiver of informed consent to both review medical records to determine eligibility, and to enroll patients in the trial.

5.2 INFORMED CONSENT PROCEDURES

Since the study population is comatose (part of inclusion criteria), their surrogates are often difficult to locate or emotionally not able to provide consent and the therapy must be provided rapidly, recruitment will be done under EFIC. Subjects will be enrolled if they meet the eligibility criteria unless they have opted out of the study previously. Surrogates (the legally authorized healthcare representative [LAR]) will be informed that subject is enrolled in a trial at an appropriate time, based on the judgement of the study team, by either study coordinator or PCAS MD. If family chooses to withdraw consent, subject will be weaned off study drug. If the subject awakens, he/she will be informed of their participation in the study and that their records were reviewed. Banking of blood for genetic studies requires a separate informed consent. The genetic sample will not be drawn until consent for the procedure has been obtained. In the event that an LAR is identified but is unable/unwilling to come into the hospital for an in-person discussion, we are requesting the option to have a physician investigator discuss the study and go through the consent over the phone. We would then email a copy of the consent to the LAR and request that he/she respond that they are agreeable for the patient to participate in the genomic

portion of the trial, or indicate that they are not agreeable. We will have two people independent of the study, usually clinical nurses or physicians, witness the process. We would then draft a Note to File to keep in the subject's study folder outlining exactly what happened, along with a copy of the entire email discussion.

In the event that the LAR is unable/unwilling to come into the hospital and does not have access to email, we are requesting a waiver to document written informed consent for the notification of study enrollment only. The physician investigator will discuss the study and will obtain permission for continued participation. A Note to File will be placed in the subject's record documenting the discussion and the LAR's response.

6. POTENTIAL RISKS AND BENEFITS

6.1 POTENTIAL RISKS

6.1.1 Risk of Experimental Drug Intervention

The known adverse events due to iNO are reviewed in the package insert and in section 2.3.3 above. Extensive safety data is available from published studies of iNO in critically ill patients with up to 2 year follow up.¹⁻⁶ In these studies rare cases of MetHb or excess nitrogen dioxide [NO₂], an airway irritant, are reported. These cases occur at doses ≥ 40 ppm. The INOVent delivery system provides constant monitoring of NO₂ levels and we will monitor MetHb to avoid toxicity. iNO may cause rebound hypoxia after prolonged use but this generally requires over 24h of use. We plan a 1h wean off the study drug to minimize this risk. Other NO donors (not iNO) can reduce blood pressure but this has not been noted in human or animal studies of iNO at the doses we plan to use. Acute kidney injury (AKI) has been noted in some clinical trials of iNO but again only with higher doses than we propose to use. We will nonetheless monitor BUN and creatinine as markers of renal function. Patients receiving iNO may experience increasing capillary wedge pressure and worsening heart failure. We will monitor oxygen requirement (FiO₂) and saturation (SpO₂) hourly during study drug administration and the PI or a physician coI will be notified of an increase of $>20\%$ in the patients' oxygen delivery (mechanical ventilator FiO₂) or a drop of > 50 mm Hg or 25% reduction (whichever is lesser) in the PaO₂ if the patient is on FiO₂ > 0.80 . This data along with any change in chest X ray (generally obtained daily in these patients) and hemodynamics collected hourly and hourly fluid intake and output will also be reviewed for each patient by the safety monitor as described above (2.3.5).

6.1.2 Risk of Study Procedures

Blood will be obtained from pre-existing indwelling catheters required as part of patient care therefore there is no additional risk from phlebotomy. Likewise urine will be collected from existing foley catheters. The total whole blood being collected is 125 ml. This represents 2.5% of the average human blood volume and is not expected to result in any significant added stress to the subjects.

6.2 ALTERNATIVE TREATMENTS

No present FDA approved therapies to provide cardiac or neuroprotection after OHCA.

6.3 POTENTIAL BENEFITS

The risks listed here are minimal in comparison to the benefits which may be gained by reducing life ending brain and heart injury.

6.4 DATA SAFETY MONITORING

6.4.1 Data Safety Monitoring Board

A Data and Safety Monitoring Board (DSMB) will be created to review this study.

6.4.2 Data Safety Monitoring Plan

Data Monitoring Plan. The proposed study will use the FDA definition of adverse events (AE) and serious adverse events (SAE). Any SAE, which is unexpected and related to study intervention, will be reported immediately to the IRB and will be followed by an additional letter detailing the nature of the SAE. In the event that a participant either withdraws from the study or the investigators decide to discontinue a participant due to a SAE, the participant will be monitored by the co-PIs until (a) a resolution is reached (e.g., the problem has resolved or stabilized with no further change expected), (b) the SAE is determined to be clearly unrelated to the study intervention, or (c) the SAE results in death. Outcomes of SAEs will be regularly reported to the IRB and the sponsor. A summary of the SAEs that occurred during the previous year will be included in the annual progress report as well as in the annual IRB renewal.

Monitoring of safety and data quality in the proposed study will be the responsibility of all personnel on the project, with primary responsibility and supervision by the Investigator. The Institutional Review Board will approve the Notification / Statement of Informed Consent (IC) for the study and provide institutional oversight of data and safety issues. The study protocol will be approved prior to recruiting or obtaining consent from any participants. Moreover, the study will be reviewed at a minimum of annual basis (or more frequently as deemed necessary) by the IRB committee. Participants will be enrolled under EFIC and the LAR (and subject assuming awakening) will be provided notification of inclusion in the study and provided the option to withdraw IC. LAR/subject will separately be requested to provide IC for retention of blood for genomics. To ensure participant safety, once participants are enrolled in the study, study staff will immediately report all adverse and serious adverse events to one of the Investigators. The Investigator will, per standardized procedures, report them to the IRB for their review. These events should also be communicated to the sponsor of the IND. With regard to monitoring of data quality and protected health information, all required personnel proposed for this project will have the required human subjects and confidentiality training, which includes information about maintaining data integrity and security. Confidentiality will be guarded using established procedures such as storing data in locked cabinets within locked offices or locked data rooms, coding by study identification numbers rather than any personally identifying information to avoid revealing the identity of subjects, and aggregating data across participants. The key linking names and study identification numbers will be kept separately from the data sets with limited access by

study personnel (RAs and principal investigator only). Only study personnel will have access to the data sets on protected servers. Oversight of all aspects of data management will occur with the Investigator.

After initial approval and at periodic intervals (at least every 6 months; to be determined by the committee) during the course of the study, the DSMB responsibilities are to:

1. Review the research protocol, informed consent documents and plans for data and safety monitoring;
2. Evaluate the progress of the study, including periodic assessments of data quality and timeliness, participant recruitment, accrual and retention, participant risk versus benefit, adverse events, unanticipated problems, performance of the trial sites, and other factors that can affect study outcome;
3. Consider factors external to the study when relevant information becomes available, such as scientific or therapeutic developments that may have an impact on the safety of the participants or the ethics of the study;
4. Review clinical center performance, make recommendations and assist in the resolution of problems reported by the PI;
5. Protect the safety of the study participants;
6. Report on the safety and progress of the study;
7. Make recommendations to the PI, and if required, to the funding agency concerning continuation, termination or other modifications of the study based on the observed beneficial or adverse effects of the treatment under study;
8. Monitor the confidentiality of the study data and the results of monitoring;
9. Assist the PI by commenting on any problems with study conduct, enrollment, sample size and/or data collection.

The DSMB will include experts in critical care medicine, pharmacology, and biostatistics. Members will consist of persons independent of the investigators who have no financial, scientific, or other conflict of interest with the study. Written documentation attesting to absence of conflict of interest will be required.

The University of Pittsburgh Office of Clinical Research, Health Sciences will provide the logistical management and support of the DSMB. A safety officer (chairperson) will be identified at the first meeting. This person will be the contact person for serious adverse event reporting. Procedures for this will be discussed at the first meeting.

The first meeting will take place before initiation of the study to discuss the protocol, approve the commencement of the study, and to establish guidelines to monitor the study. The follow-up meeting frequency of the DSMB will be determined during the first meeting. An emergency meeting of the DSMB will be called at any time by the Chairperson should questions of patient safety arise.

The DSMB will meet prior to the beginning of enrollment and every 6 months until study completion (planned at 2 years). A planned interim analysis will be conducted at 1 year or after 60/130 subjects is enrolled, whichever occurs first.

6.4.3 Parameters to be Monitored

The following progress will be monitored throughout the course of the research to ensure the safety of subjects as well as the integrity and confidentiality of their data.

- An evaluation of the progress of the research study, including subject recruitment and retention, and an assessment of the timeliness and quality of the data.
- A review of collected data (including adverse events, unanticipated problems, and subject withdrawals) to determine whether there is a change to the anticipated benefit-to-risk assessment of study participation and whether the study should continue as originally designed, should be changed, or should be terminated.
- An assessment of external factors or relevant information (eg. pertinent scientific literature reports or therapeutic development, results of related studies) that may have an impact on the safety and study participants or the ethics of the research study.
- A review of study procedures designed to protect the privacy of the research subjects and the confidentiality of their research data.

The severity of adverse changes in physical signs or symptoms will be classified as follows:

- Grade 1 (Mild): asymptomatic or mild symptoms; clinical or diagnostic observation only; intervention not indicated.
- Grade 2 (Moderate): minimal, local or noninvasive intervention indicated; limiting age-appropriate ADL (Activities of Daily Living).
- Grade 3 (Severe): medically significant but not immediately life-threatening; hospitalization or prolongation of hospitalization indicated; disabling; limiting self care ADL.
- Grade 4 (Life-threatening): consequences; urgent intervention indicated.
- Grade 5 (Death): event is a direct cause of death.

6.4.4 Frequency of Monitoring

The Investigator will review subject safety data as it is generated. The Investigator, sub-investigators, and the research staff will meet on a **monthly** interval to re-evaluate study goals, subject recruitment, data coding and retention, documentation and identification of adverse events, complaints and confidentiality of subjects. There will be an evaluation of the progress of the research study, including assessments of data quality, time lines, participant recruitment, accrual, and retention. The Investigator will also review the outcome and adverse event data to determine whether there is any change to the anticipated benefit-to-risk ratio of study participation and whether the study should continue as originally designed or

should it be re-evaluated and changed.

Independently the safety monitor will be review clinical data from the study consisting of subject VS, vasopressor and inotrope use and labs at baseline and during the first 24 h of enrollment (which includes study drug dosing) and final outcomes. This review will occur at least every 4 weeks. In the event of a SUAE, the safety monitor will review the record within 48 h, breaking the blind to determine whether this is a drug associated SUAE

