- *Best estimate of CPC pre-OHCA (if no surrogate is present and no medical records are found on the subject this will be assumed to be CPC 1)
- *Best estimate of mRS pre-OHCA ((if no surrogate is present and no medical records are found on the subject this will be assumed to be mRS 0)
- Rib fracture after ROSC
- Sternal fracture
- Witnessed aspiration
- Infection present at baseline
- Infection type
- Sputum color
- Vent mode
- Set Tidal Volume (V_t) or Inspiratory Pressure (P_{insp})
- Positive end expiratory pressure (PEEP)
- Fraction of inspired oxygen (FiO₂) expressed as % oxygen
- Peak Pressure (PIP)
- Plateau Pressure (P_{plat})
- Chest X-Ray reading possibly consistent with pneumonia
- Positive airway culture

Toxicology report

Cause of arrest

History of drug/alcohol use

Current drug/alcohol use

- ECHO RESEARCH ONLY To be performed by PCAS physician or research assistant trained by [name], who is a cardiologist and Associate Professor of Medicine at the University of Pittsburgh.
 - o Tricuspid valve regurgitant velocity
 - o Aortic valve velocity (CO estimate)
 - o Pulmonary valve velocity
 - o Tricuspid annular plane systolic excursion (TAPSE)
 - o LVEF
- *LSCI RESEARCH ONLY To be performed by a research assistant trained by the PI. A complete description is available in section CS10.1.
 - o Baseline blood flow and RH after 1 min vasoocclusion [resolution 1 image/s; 10 image/s averaging]
 - o Baseline blood flow and RH after 5 min vasoocclusion [begin 5 min after last test]*
 - *Baseline labs (troponin, arterial blood gas, lactate, plasma nitrite level,)
 - Additional plasma labs (neuron specific enolase, platelet mitochondria, ascorbate, cardiolipin, SNO, cGMP, plasma banking)
 - Urine labs (renal failure and nitrated fatty acid measurements)
 - Blood for genomics (retained unless informed consent declined)
 - *Baseline vital signs VS (temperature, heart rate [HR], mean arterial blood pressure [MAP], arterial oxygen saturation [SpO2])

STUDY DRUG (0-12 h) DATA

(Refer to Chart below)

- *Every 3 hour vital signs VS (temperature, HR, MAP, SpO2)
- Hourly monitoring of VS, SAEs, vent settings
- Pulmonary Arterial Pressures (systolic, diastolic, mean) – often not available
- Central Venous Pressure – often not available
- SvO2 – often not available
- *Plasma labs at 6 and/or* 12 h (troponin, arterial blood gas, lactate, methemoglobin, plasma nitrite level)

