***Methemoglobin to be collected at 6 hours only**

DAY 1-3 (0-72 h post-ROSC) DATA

During post-ROSC days 1-3, the following data elements will be collected by a physician coinvestigator/research assistant prospectively or by a research assistant retrospectively. Refer to chart for visual of when labs will be drawn.

- Plasma labs measured variably between 24 and 72 h (troponin, arterial blood gas, lactate, plasma nitrite level, neuron specific enolase, ascorbate, cardiolipin, plasma banking)
- Urine labs measured variably between 24 and 72 h (renal failure and nitrated fatty acid measurements)
- *Full Outline of UnResponsiveness (FOUR) Score (components below)
- Eyes
- Motor
- Brainstem
- Reflex
- *Glasgow Coma Score (GCS)
- Eyes
- Verbal
- Motor
- EEG interpretation
- Dominant background present
- Reactivity present
- Seizures present
- Seizure type
- Burst-suppression ratio
- Estimate of survival to hospital DC
- Median nerve SSEP
- Witnessed aspiration
- New suspected infection last 24h
- Infection type
- Sputum color
- Vent mode
- Set Vt
- Set PC
- PEEP
- FiO2 (Use % oxygen)
- Peak Pressure
- Plateau Pressure
- CXR last 24h read may be pneumonia
- Positive airway culture last 24h

- Vital Signs (VS) (highest and lowest for each)
- Time to follow commands (assigned once)
- SOFA (worst in prior 24h period; some components may be missing)
- Respiratory (when no PaO₂ is available for PaO₂:FiO₂ ratio, use SpO₂:FiO₂ ratio)
- Nervous (based on GCS below)
- Cardiovascular
- Liver
- Coagulation
- Renal
- Interventions
- Coronary angiography
- PCI
- ECMO
- CPR
- CABG
- Mechanical ventilation hours
- NIPPV hours
- 24h FiO₂ AUC
- Tracheostomy
- Medications (dichotomous for use not dose)
- Alteplase
- Anti-epileptic
- Midazolam infusion
- Intermittent Benzodiazapine
- Propofol infusion
- Intermittent Propofol
- Opiate infusion
- Intermittent opiate
- Neuromuscular blockade infusion
- Intermittent neuromuscular blockade
- Neurostimulants
- *Vasopressors
- *Inotropes
- Ketamine
- Steroids (hydrocortisone/methylprednisolone)
- Cumulative vasopressor index (CVI; worst in prior 24h period)
- *BUN (highest value in prior 24 h)
- *Creatinine (highest value in prior 24 h)
- Hb
- WBC
- platelets
- PT
- INR
- PTT
- Bilirubin
- AST

- ALT
- BNP
- SvO2 (%)
- venous PaO2
- venous PaCO2

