2.3.3. Dose Selection

A number of studies have reviewed the safety of iNO in adults primarily in the setting of acute respiratory distress syndrome (ARDS). A recent meta-analysis found improved oxygenation but also greater acute kidney injury (AKI) resulting from iNO use.²⁵ When this was examined by dose, AKI only resulted in those patients receiving higher cumulative doses of iNO (≥ 40 ppm for ≥ 48 h).²⁶ Our study will limit iNO to 20 ppm for 12h hence AKI is not expected though we will track BUN and creatinine on all subjects. A separate meta-analysis examining effects of iNO in

acute hypoxic respiratory failure in adults and children found no associated adverse events.²⁷ A study of iNO used in transport identified no adverse events associated with the drug.²⁸ Although iNO significantly increases methemoglobin (metHb) levels, the increase (0.3%) is clinically insignificant and not associated with toxicity²⁹ which is uncommon until levels of 20-30% (we will consider > 10% a significant and unexpected adverse event). The best predictor of significant metHb >4% (as < 0-3% is considered within normal range) is cumulative iNO dose of >2000 ppm * h.³⁰ In our study subjects will receive only 250 ppm * h. We will monitor methemoglobin as part of our study at 6h. Although iNO lowers pulmonary blood pressure it has not been linked to reduction in systemic arterial blood pressure. We will monitor blood pressure effects closely in our study given the inherent instability of cardiac arrest subjects.

Effects of iNO after cardiac arrest has been studied in 4 preclinical animal studies.⁸⁻¹¹ These published studies demonstrated benefit using iNO 40 ppm started within 2h of ROSC which is additive to therapeutic hypothermia⁸ as well as neuroprotection without temperature control.⁹ These animal models include mouse and pig models of asystole and ventricular fibrillation (VF). In addition iNO has been shown to protect in animal models of focal heart¹²⁻¹⁵ and brain¹⁶⁻¹⁹ injury. This is important since most of the mortality and morbidity after OHCA results from heart and brain injury.²⁰

Animal models of asphyxia²¹ and other focal brain ischemia reperfusion models demonstrate NO deficiency early in reperfusion lasting at least 6h and benefits from iNO.^{16,19}

Information from prior clinical trials of iNO are available by cross reference in the Mallinckrodt NDA 20-845 (letter authorizing cross reference is included with application).

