 - Arterial hypotension with a systolic blood pressure $\leq 90 \text{ mmHg}$ or mean arterial blood pressure $\leq 65 \text{ mmHg}$ for at least one hour despite adequate fluid loading not explained by other causes of shock (Grade 4);

- Renal dysfunction with urine output ≤ 0.5 mL/kg/h for at least one hour despite adequate fluid loading or serum creatinine above 200 $\mu\text{mol/L}$ (2.3 mg/dL) [Grade 3];
 - Metabolic acidosis with base deficit ≥ 5.0 mmol/L or serum lactate ≥ 1.5 fold above local reference range (2.4 mmol/L at UPMC) [Grade 3].
- Pneumonitis assessed as the presence of air bronchograms on any chest x-ray within one week of the index cardiac arrest. (Grade 3)
- Since many of these comatose OHCA subjects will receive therapeutic hypothermia, anticipated SAE include:
 - Electrolyte abnormalities: defined as the presence of any of the following from induction of hypothermia until 72 hours (all Grade 3):
 - Hypokalemia assessed as serum potassium concentration < 3.5 mmol/L.
 - Hyperglycemia assessed as serum glucose > 240 mg/dL.
 - Hypophosphatemia assessed as serum phosphate concentration < 0.8 mmol/L.
 - Hypocalcemia assessed as serum ionized calcium < 2.2 mmol/L.
 - Bleeding (overt bleeding with Hb drop > 3 g/dL or transfusion; cardiac tamponade; bleeding requiring surgical intervention for control or intravenous vasoactive agents; intracranial hemorrhage; intraocular bleed compromising vision; operation for vascular closure for the purpose of controlling bleeding; fatal bleeding) [Grade 3]
 - Thrombosis (Grade 3)
 - Infection (Grade 3)
 - Fluid shifts defined as net fluid intake/output exceeding 3 L positive or negative in a 24h period (Grade 3)
- Pulmonary Edema: We shall monitor the incidence of pulmonary edema in each treatment duration group and assess whether there is a significant difference between groups. It will be defined as the presence of congestive heart failure on a hospital-based chest x-ray (first emergency department or ICU chest x-ray). OHCA is more common in patients with cardiomegaly, and this radiographic sign alone will not be a criterion for diagnosis of acute heart failure. (Grade 3)

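### Kidney safety is tracked with no named pre-drug creatinine and no change-based event, and the plan disagrees with itself on whether day 2–3 values reach the safety monitor

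*Combined protocol and SAP*

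**What the plan says.** **Risk.** Section 6.1.1 states that "Acute kidney injury (AKI) has been noted in some clinical trials of iNO", and adds that this was seen only above the doses planned here. Section 2.3.3 ties it to at least 40 ppm for at least 48 h and concludes: "hence AKI is not expected though we will track BUN and creatinine on all subjects".

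**Baseline.** The starred (essential) baseline item in section 2.2 reads "Baseline labs (troponin, arterial blood gas, lactate, plasma nitrite level". BUN and creatinine are not in it, and Table 1 has no row for either. Two other baseline entries come close. One is an unstarred line, "Urine labs (renal failure and nitrated fatty acid measurements", sampled at 0, 12 and 24 h. The other is a generic retrospective entry for clinical laboratory data in the visit table, with no analytes named.

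**Follow-up.** The day 1–3 list in section 2.2 stars BUN and "Creatinine (highest value in prior 24 h". Day 1 is counted from ROSC, not from the start of study drug.

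**Event.** Section 6.4.5 defines renal dysfunction as urine output at or below 0.5 mL/kg/h "for at least one hour despite adequate fluid loading or serum creatinine above 200" µmol/L (2.3 mg/dL). Section 2.5.4 says the listed safety outcomes will be tabulated and tested with exact methods.

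**Review.** Section 6.4.4 has the safety monitor look every four weeks or more often at "labs at baseline and during the first 24 h of enrollment", plus final outcomes. Sections 2.3.5 and 6.5.2 describe the same four-weekly review of labs with no 24 h limit.

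**The concern.** Creatinine tracking is the plan's stated answer to a named drug risk, so it should be able to separate a rise after study drug from kidney function that was already poor. As listed, it cannot do this for an individual subject. There is no named value to subtract, and the first value recorded may itself predate the drug.

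The event definition has the same weakness at the level of the arms. A subject with long-standing elevation scores as an event on either treatment, and a subject with a large rise from a normal value may not score on creatinine. The same adverse event list uses change criteria elsewhere (a platelet fall of more than 30%, a haemoglobin fall of more than 3 g/dL), so an absolute renal cut-off is not a convention applied throughout.

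The review window matters because renal dysfunction is listed as an expected event, and the expedited route is tied mainly to methemoglobin above 10%. A renal signal is therefore more likely to surface through routine review than through the 48 h review. If 6.4.4 governs, the one independent person looking every four weeks does not receive most of the creatinine the plan treats as essential.

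**Working it through.** **Inputs.** Cut-off 200 µmol/L, printed as 2.3 mg/dL (6.4.5). Study drug within 4 h of ROSC (2.1). Day 1 is 0–24 h from ROSC, and creatinine is collected to 72 h (2.2). Dose 20 ppm for 12 h plus a 1 h wean, stated as 250 ppm·h (2.3.3). Assumption not in the documents: 88.4 µmol/L per mg/dL.

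**1. Reproduce the plan's figures.**
- Cut-off: 200 / 88.4 = 2.26, which rounds to the printed 2.3 mg/dL.
- Exposure: 20 × 12 = 240; wean (10+5+4+3+2+1) × 10/60 = 4.2; total 244.2 ppm·h, consistent with a rounded 250.
- Exposure at which 2.3.3 places kidney injury: at least 40 × 48 = 1,920 ppm·h. 250 / 1,920 = 0.13, so planned exposure is about 13% of that level.

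**2. Is there a pre-drug serum value?** It is absent from the starred baseline labs, the additional plasma labs and Table 1. The generic retrospective entry might include it but does not say so. The day 1 maximum covers 24 h from ROSC, of which up to 4 h (4/24, one sixth) can precede the drug. If the peak falls in that part, it is a pre-drug value recorded as a day 1 value. Change from baseline therefore cannot be derived from the items as listed.

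**3. What the creatinine limb detects.** Fold rise needed = 2.3 / baseline, over assumed baselines (the documents give none):

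| Baseline (mg/dL) | Fold rise needed |
|---|---|
| 0.6 | 3.8 |
| 0.8 | 2.9 |
| 1.0 | 2.3 |
| 1.5 | 1.5 |
| 2.0 | 1.15 |
| 2.4 | already above before drug |

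A doubling is not counted when 2 × baseline ≤ 2.3, that is, when baseline ≤ 1.15 mg/dL (1.13 using 200 µmol/L exactly, 2.26 / 2). For example, a move from 1.0 to 2.2 is a 120% rise and is not a creatinine event.

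**4. Effect on the between-arm test.** Let *f* be the share of subjects who meet the criterion whatever the drug does, equal in the two arms by randomisation, and *q* the event probability among the rest. Then each arm's rate is p = f + (1 − f)q, and the difference is (1 − f)(q_iNO − q_placebo). The difference shrinks by the factor (1 − f) and the ratio moves toward 1. Rises that stay below the cut-off are absent from *q*. The documents give no *f*, so the dilution has a direction but no computed size.

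**5. Review window under 6.4.4.** Taking enrolment as the start of drug at 0–4 h after ROSC, the 24 h window closes at 24–28 h after ROSC. Collection runs to 72 h, so 72 − 28 = 44 h to 72 − 24 = 48 h of collected values lie outside it. Dosing plus wean lasts 13 h, so the window includes 24 − 13 = 11 h after the drug is off.

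**The case against.** A good deal can be said for the plan.

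- **Late values are collected and seen.** A reader might infer from 6.4.4 that rises after 24 h go undetected. The documents do not support that. BUN and creatinine are starred to 72 h, with complete data expected. The investigator reviews safety data continuously, and 6.4.4 adds a monthly staff meeting that covers adverse events. The DSMB meets every six months, can be called in an emergency, and reviews all data at 12 months or 60 subjects. Sections 2.3.5 and 6.5.2 may already give the monitor the later labs.
- **Wider labs would not by themselves show an excess by arm.** Nothing says the monitor's routine review is unblinded; unblinding follows a concern or a qualifying event. This stands. However, the investigators are blinded too, and the monitor may unblind, so it still matters whether the monitor receives these values.
- **Randomisation protects the group comparison.** It would be too strong to say the plan cannot measure a drug effect on the kidney. Daily peak creatinine can be compared between arms under 2.5.2 without a baseline. There are also urine markers at 0, 12 and 24 h and a daily renal SOFA component. This stands for group averages. It does not repair the dichotomous event that 2.5.4 tests, and none of these gives a change in serum creatinine.
- **The prior risk is low.** Planned exposure is about 13% of the level at which 2.3.3 says injury occurred. This limits how much is at stake.
- **The urine-output limb may catch some subjects the creatinine limb misses.** That is possible, but a single low hour is also common ground for both arms and carries no baseline either.

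**Conclusion.** The point holds as a modest, cheaply corrected weakness in measurement, together with an internal inconsistency. It does not show that renal harm would go unseen.

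Three statements are supported by the text. No list names a pre-drug serum BUN or creatinine, and the day 1 maximum mixes pre-drug and on-drug time. The renal event is absolute, so it counts pre-existing elevation in both arms and can miss a doubling from about 1.15 mg/dL or lower on creatinine, which dilutes the planned test. Section 6.4.4 conflicts with 2.3.5 and 6.5.2 on whether day 2–3 labs are in the safety monitor's review; under 6.4.4 alone, 44–48 h of collected values are not.

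The sizes rest on the standard creatinine conversion, on illustrative baselines, and on taking enrolment as the start of study drug. The loss of sensitivity in the exact test cannot be quantified, because the documents give neither baseline renal function nor the expected frequency of low urine output.

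**What to change.** 1. Add the last BUN and creatinine before study drug, abstracted from the chart, to the starred baseline list in section 2.2.
2. Add a renal safety outcome to 2.5.4: the rise from that value to the highest creatinine after drug start through day 3. Record the day 1 maximum so that only values after drug start contribute. Any categorical threshold should be fixed before unblinding. Report this alongside the existing absolute criterion, which stays as it is.
3. State a fallback for subjects with no pre-drug value, for example that they contribute to the absolute criterion only and are counted by arm.
4. Reconcile 6.4.4 with 2.3.5 and 6.5.2 so that the monitor's four-weekly packet explicitly includes the day 1–3 BUN and creatinine already collected.

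The cost is one pair of charted values per subject, one definition, one reconciled sentence and two more days of existing labs in the monitor's packet. No new sampling is needed beyond routine chemistry, and no treatment rule changes. The small drawback is the fallback group, whose size is not known in advance.
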